Participants: 110 patients (55 per group) with PD-MCI will be recruited for this study as well as 110 identified and consistent caregivers of the participants. All caregivers will be asked to complete several questionnaires regarding the participant's quality of life and daily functioning prior to the intervention, at follow-up visits, and after the intervention. Although attrition did not occur in Phase I, over-recruitment by 20% will be instituted to account for possible subject attrition or unusable data. Participants will receive a payment of \$40 for each of the four assessments they complete (pre- and post-intervention/support and 6- and 12-month follow-ups).

Procedures: We will primarily recruit Veterans with PD from the VASDHS Neurology and Neuropsychology Clinics. While we will attempt to exhaust recruitment at VA clinics first, recruitment of women may be limited at the VA, and therefore, we will likely need to recruit from outside clinics to obtain a PD-epidemiologically accurate gender ratio of 60 (men)/40 (women). In this regard, we will primarily recruit from the University of California, San Diego (UCSD) Movement Disorders Center. Referred participants will be screened for inclusion/exclusion criteria (please see above) and consented if appropriate. All participants will have Level II MDS-criteria based diagnosis of MCI derived from a formal neuropsychological evaluation within the past 12 months. As most participants will be referred from the VASDHS and UCSD Movement Disorder Center, the majority will have MDS-criteria MCI diagnoses prior to referral. However, should a PD patient be referred for this study who has not had formal neuropsychological testing or if testing is outdated (>12 months), pre-inclusion neuropsychological testing will be performed through [name] lab, which follows patients neuropsychologically. Likewise, if the WRAT-4 Reading scale has not been administered within the past year, this 2-5 minute measure will also be administered to ensure adequate reading level. To avoid confounds, no test proposed as outcome measures in this study will be used to determine the PD-MCI diagnosis.

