Upon meeting study criteria, participants will be randomized to one of two 10-week conditions (CogSMART-PD or Supportive Care). Randomization will occur in blocks (i.e., first 5 people enrolled will be assigned to the intervention group, next 5 will be assigned to control group, next 5 will be assigned to the intervention group, and so on until the sample size of 55 per group is met). Within one to 1.5 weeks prior to beginning the group, participants will be tested by a research assistant blinded to group assignment on a 2-2.5 hour

battery of cognitive, neuropsychiatric, health status/QoL, and strategy use measures as well as a motor assessment (UPDRS-Part III), which will immediately precede the cognitive assessment (please see Assessment/Materials). Participants will be tested in the “on-state” of parkinsonian medications to limit confounding variability (e.g., of motor symptoms, such as tremor) on test results. All participants will be tested at the same time, preferably in the morning, if possible. Breaks will be given during the assessment as needed. Groups will consist of 5 individuals with PD-MCI and be led by a trained clinician (who is not involved in the clinical care or assessment of these participants). Following the intervention and 6- and 12-months post-intervention, PD-MCI participants will be re-tested by a group-blinded research assistant. 24 months post-intervention, participants will be asked to complete a brief (15 minute) telephone interview regarding changes in health status or living situation since the 12-month follow up. Following the 12-month follow-up, the control (support) group will be permitted to join CogSMART-PD.

Assessment/Materials: Outcome measures were carefully selected so that they: 1) represent areas that are frequently impaired, dysfunctional, or problematic for individuals with PD-MCI; 2) correspond to domains that are targeted for improvement by the CogSMART-PD intervention; 3) have adequate psychometric properties for use in PD; and 4) have shown utility and applicability based on the pilot and preliminary studies. Total neuropsychological and motor testing time is estimated to be 2-2.5 hours.

Cognitive Function and Cognitive Strategy Assessment:

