Monitoring Plan. As individuals with PD are at high risk for falls, we will carefully screen all individuals for history of falls upon recruitment. We will use the baseline UPDRS falling item (#13) in which a history of falls is categorized on a likert scale from 0 (none) to 4 (falls >once per day). A history of falls as assessed by the UPDRS appears to be one of the best predictive methods of subsequent falls at this time⁸⁰. Those individuals who endorse a history of falling or score >0 on the UPDRS falling item, will be closely monitored. This includes ensuring that they are escorted to and from the intervention room from their vehicle as well as to and from the bathroom, as needed. Should a patient need help within the bathroom,

a caregiver will be requested to assist. If needed, we will utilize the VA escort service. Although not common in PD, all participants will also be assessed for suicidal ideation/intent at baseline, as standard of care for psychological/behavioural interventions. If suicidal ideation is acknowledged, indicated by a score of 2 or greater on item 9 of the Beck Depression Inventory-II (BDI-II), research participants will be referred directly to a VA-privileged clinician for further evaluation. These participants will be monitored for changes in mood during the intervention.

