such information arise that causes study staff to be concerned about that participant's psychological well being, appropriate referrals to the VASDHS Geropsychiatry Clinic or other appropriate community referrals will be made. As individuals with PD are at a high risk for falls, we will carefully screen all individuals for history of falls upon recruitment. We will use the baseline UPDRS falling item (#13) in which a history of falls is categorized on a likert scale from 0 (none) to 4 (falls >once per day). A history of falls as assessed by the UPDRS appears to be one of the best predictive methods of subsequent falls at this time. Those individuals who endorse a history of falling or score >0 on the UPDRS falling item, will be closely monitored. This includes ensuring that they are escorted to and from the intervention room from their vehicle as well as to and from the bathroom, as needed. Should a patient need help within the bathroom, a caregiver will be requested to assist. If needed, we will utilize the VA escort service. Although suicide is an extremely minimal risk factor for PD patients, suicidal ideation/intent will be assessed at baseline. Any indication of suicidal ideation will be brought to licensed and privileged supervisor's immediate attention. All intervention group participants will be provided with the class manual and so if there is a need for early termination with no opportunity to join another group, those individuals will still have the psychoeducation materials. In general, the study poses no significant increase in risk than what would normally be present in proper clinical management and psychological treatment of PD-MCI patients.

A tertiary risk might include unintentional disclosure of confidential test information, but confidentiality will be strictly maintained in data storage, manipulation, and presentation. Participant identity will be coded immediately upon entry into the study, and neither the participants' names nor any identifying information will be present in the data set. Presentation of the results will involve group data and the subjects' identity will not be disclosed.

MRI neuroimaging

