Test anxiety, boredom and fatigue will be minimized by explaining the testing procedures, by supportive assurance, and by taking brief rest periods throughout the two-2.5 hour evaluation. Evaluations will be performed by examiners experienced in working with geriatric and neurologic populations and will be able to gauge when breaks are needed or when testing may need to be rescheduled or cancelled due to severe fatigue or anxiety. To minimize potential discomfort during the UPDRS motor exam, study staff will briefly explain the nature and purpose of the exam before beginning, and will instruct subjects to ask questions or communicate if they are unsure about or uncomfortable with any portion of the exam. Additionally, subjects will sign and receive a copy of the consent addendum, which has further details about the exam, prior to the exam. Each CogSMART-PD session will last approximately 1.5 hours and breaks are offered throughout the session as well. As individuals with PD are at a high risk for falls, we will carefully screen all individuals for history of falls upon recruitment. We will use the baseline UPDRS falling item (#13) in which a history of falls is categorized on a likert scale from 0 (none) to 4 (falls >once per day). A history of falls as assessed by the UPDRS appears to be one of the best predictive methods of subsequent falls at this time. Those individuals who endorse a history of falling or score >0 on the UPDRS falling item, will be closely monitored. This includes ensuring that they are escorted to and from the intervention room from their vehicle as well as to and from the bathroom, as needed. Should a patient need help within the bathroom, a caregiver will be requested to assist. If needed, we will utilize the VA escort service. Although not common in PD, all participants will also be assessed for suicidal ideation/intent at baseline, as standard of care for psychological/behavioural interventions. If suicidal ideation is acknowledged, indicated by a score of 2 or greater on item 9 of the Beck Depression Inventory-II (BDI-II), research participants will be referred directly to a VA-privileged clinician for further evaluation. These participants will be monitored for changes in mood during the intervention.

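### In the visible text, Phase II schedules its suicidal-ideation question once, at baseline; repeating it at the three later in-person visits would be a cheap improvement

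*Combined protocol and SAP*

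**What the plan says.** Three places in the protocol deal with suicidal ideation in Phase II.

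- Section 9, Phase II, Monitoring Plan: "Although not common in PD, all participants will also be assessed for suicidal ideation/intent at baseline, as standard of care for psychological/behavioural interventions". A score of 2 or more on BDI-II item 9 leads to referral to a VA-privileged clinician. For those referred, the plan adds: "These participants will be monitored for changes in mood during the intervention".
- Section 14, Phase II: "Although suicide is an extremely minimal risk factor for PD patients, suicidal ideation/intent will be assessed at baseline". It continues: "Any indication of suicidal ideation will be brought to licensed and privileged supervisor's immediate attention". No score threshold and no time limit are attached to this sentence.
- Section 15, Phase II, repeats the Monitoring Plan: "all participants will also be assessed for suicidal ideation/intent at baseline", with the same item 9 threshold and referral.

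The visit schedule is in Section 9, Phase II. Participants are paid for the "four assessments they complete (pre- and post-intervention/support and 6- and 12-month follow-ups". Baseline testing takes place "Within one to 1.5 weeks prior to beginning the group", and the group then runs for 10 weeks. After the group, and again 6 and 12 months after it, "PD-MCI participants will be re-tested by a group-blinded research assistant". A 15-minute telephone interview about health status and living situation follows at 24 months.

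Section 9.8 lists the BDI-II among the questionnaires but gives no visits for it. The Phase II instrument descriptions in Section 9 do not include it.

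**The concern.** The trial follows people with PD-MCI for more than a year after baseline. Section 7 says depression is more common in this group than in PD with normal cognition. Hypotheses 2 and 3 test neuropsychiatric symptoms at 10 weeks, 6 months and 12 months, so the sponsor treats these symptoms as able to change. Yet the only direct question about suicidal ideation that the visible text schedules comes before the group starts.

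What is at stake is patient safety, not the analysis. Ideation that begins after baseline can still come to light, but only through an unscheduled route. The protocol asks this question of everyone once, with a referral rule, and does not say why once is enough. The Section 15 prompt lists how often safety data are collected among the details to give when applicable. For ideation, the Phase II answer gives baseline only.

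**Working it through.** The plan states no interval of its own, so there is no figure to reproduce. The check is calendar arithmetic on the Phase II schedule, followed by a reading of the other safeguards.

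**Inputs (Section 9, Phase II)**
- Lead from baseline testing to group start: 1 to 1.5 weeks.
- Group: 10 weeks.
- Follow-up visits: 6 and 12 months after the intervention, taken as 26 and 52 weeks.
- Telephone interview: 24 months after the intervention, taken as 104 weeks.
- Assumptions: item 9 is asked at the baseline testing visit, and the post-intervention visit falls at the end of the 10 weeks, since no window is given.

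**As written: one scheduled question, at week 0**
- To the 12-month visit: 1 + 10 + 52 = 63 weeks; 1.5 + 10 + 52 = 63.5 weeks.
- To the telephone interview: 1 + 10 + 104 = 115 weeks; 1.5 + 10 + 104 = 115.5 weeks.

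**With item 9 at the three later visits: four scheduled questions**
- Baseline to post-intervention: 1 + 10 = 11 to 1.5 + 10 = 11.5 weeks.
- Post-intervention to 6 months: 26 weeks.
- 6 to 12 months: 52 − 26 = 26 weeks.
- Longest interval between questions: 26 weeks.
- Last question to the telephone interview: 104 − 52 = 52 weeks.

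**Sensitivity**
- Calendar months instead of 4-week approximations: up to 63.7 weeks as written and 26.1 weeks with the fix.
- Post-intervention visit at the tenth weekly session: 1 + 9 + 52 = 62 weeks.
- Follow-up counted from baseline, as in Phase I: about 52 weeks as written and 26 with the fix. Section 9, Phase II, counts from the end of the intervention, so this is not the main case.

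**What else could pick up ideation after baseline**
- Mood monitoring (Sections 9 and 15): only participants flagged at baseline, and only during the intervention.
- Weekly groups with a trained clinician (Section 9) and weekly participant and clinician evaluations (Section 9.11): confined to the 10-week group period. The evaluations serve treatment fidelity.
- Referral when staff become concerned (Section 14): depends on information coming up, and the same section does not expect members of the rehabilitation group to disclose mental-health matters.
- Escalation of any indication to the supervisor (Section 14): has no end date, but needs an indication to act on.
- NPI-Q (Section 9): asks about depression and probes positive answers. No ideation item or referral threshold is described.
- Exclusion of untreated current major depression or anxiety disorder (Section 10): acts at entry. Treated depression stays eligible.

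None of these is a scheduled ideation question after baseline.

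**The case against.** The strongest case against acting is that the visible text may not be the whole plan. Section 9.8 lists several instruments that appear in neither phase's narrative battery, such as the sleep, fatigue and falls-efficacy scales, so the battery actually given may be wider than Section 9 describes. The BDI-II is not in the Phase I battery, which points to Phase II use, and repeated use would fit Aim 2. Some pages are not public, and the Section 3.3 tick boxes on a monitoring board or safety plan cannot be read. This stands. It limits the claim to what the visible text schedules, and the fix allows for it.

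The sponsor also gives a low-risk rationale: ideation is described as uncommon in PD and a very small risk, and untreated major depression is excluded. The documents show no mechanism by which either arm raises the risk, and nothing in them requires a repeat. This also stands and sets the priority. It does not explain why the question is asked only once.

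Two stronger readings are tempting. A reader might infer that ideation arising after baseline would go undetected or unmanaged. The documents do not support that: Section 14 escalates any indication without a time limit and provides for referral, and weekly clinician contact runs through the group period. What is missing is a scheduled prompt. A reader might also take 63 weeks as an interval between questions. With one question there is no such interval; 63 weeks is the time from the only question to the last in-person visit.

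**Conclusion.** The point holds as an optional, modest-priority improvement to the monitoring plan. In the visible text the ideation question is scheduled once, about 63 weeks before the last in-person visit and about 115 weeks before the 24-month call. Repeating it at the three later visits would make the longest interval between scheduled questions about 26 weeks, with about 52 weeks from the last one to the call.

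These figures rest on the post-intervention visit falling at the end of week 10 and on follow-up being counted from the end of the intervention. The documents give no rate of new ideation, so the number of cases found earlier cannot be stated. Given the sponsor's view of the risk and the entry exclusion, it is probably low. The change would add three point-in-time screens, not continuous surveillance. It is not evidence of an error in the plan, and it touches no endpoint, sample size or analysis.

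**What to change.** In the Section 9 Monitoring Plan, with matching text in Sections 14 and 15, state that BDI-II item 9 is repeated for all Phase II participants at the post-intervention, 6-month and 12-month visits.

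Keep the existing rules and say how they fit together. A score of 2 or more triggers the referral to a VA-privileged clinician already set out in Sections 9 and 15. Any lesser indication goes to the licensed supervisor, as Section 14 already requires. The hand-off carries the subject number and the answer but not the group, so the research assistant stays blinded. The stretch to the 24-month call stays uncovered unless the investigators also add the item there.

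If the BDI-II is already repeated, or a separate safety plan covers this, cite it in the Monitoring Plan instead.

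Cost: 110 × 3 = 330 single items, or 132 × 3 = 396 with the 20% over-recruitment. If the 60 fMRI participants and up to 10 Wii and 10 Odoroki participants are additional and attend every visit, the ceiling is (132 + 60 + 20) × 3 = 636. At an assumed 2 to 5 minutes per item, which the documents do not give, that is 330 × 2/60 = 11 to 330 × 5/60 = 27.5 staff hours for 330 items, and 636 × 2/60 = 21.2 to 636 × 5/60 = 53 hours at the ceiling. Per visit it is between 2/150 = 1.3% and 5/120 = 4.2% of a 2 to 2.5 hour session. These hours are for item 9 alone; giving the whole BDI-II would take longer. Clinician time for positive answers and the protocol wording come on top.

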Our projected sample size is consistent with the sample reported on in the preliminary data section ([name] et al., 2008). As we propose to use a similar sample size and the same cognitive rehabilitation program, we anticipate achieving similar medium to large effect sizes in the proposed study. To determine whether CogSMART will improve cognition in PD, we will employ statistical analyses including reliable change indexes to take into account change in neuropsychological test scores over the course of the intervention while also accounting for predicted practice effects. We will compare the treatment and control groups on baseline and three-month change scores. Group comparisons of differences and

changes in neuropsychological test scores between as well as within groups will also be determined via repeated measures (RM) ANCOVAs. Cognitive, functional, and quality of life indices of both participants and caregivers will be of interest in determining efficacy of treatment.

As an exploratory aim, we will recruit 60 additional individuals to complete the protocol as described above and in addition, participate in two (pre/post) hour-long brain imaging (fMRI) sessions. The imaging sessions will consist of a structural brain scanning and participation in an fMRI cognitive task (please see below). Following the baseline evaluation, half of the participants will be randomly assigned to the intervention group ($n = 30$) and participate in the CogSMART program. The groups will be broken up to consist of 8-10 individuals. The remaining participants ($n = 30$) will be assigned to the non-intervention /waitlist ("care-as-usual") group. This group will also be broken down into groups of 8-10 when enrolled in the intervention. Participants will be retested by a group assignment-blinded examiner on the clinical and cognitive battery and imaging protocol following the intervention or waitlist.

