4. Informant Questionnaire on Cognitive Decline in the Elderly (IQCODE)³⁹. The IQCODE is a 26-item, 5-minute informant-based questionnaire used to assess the patient’s everyday functional-based measure of cognition (e.g., recognizing familiar faces, remember things in general, handling financial matters) on a 5-point scale (1=much improved to 5=much worse). The IQCODE has been used fairly extensively in individuals with cognitive impairment and has been found to have high reliability and good validity⁵². In addition, we will also administer the self-report version the IQCODE (IQCODE-SR) to the patients. A psychometric study of the IQCODE-SR found it to have good feasibility, homogeneity, and construct validity⁶⁷. The IQCODE has been used as an outcome in several seminal PD studies (e.g., Aarsland et al., 2009⁶⁸). We conducted a validation study (manuscript in preparation), of the IQCODE in 100 PD patients and found it to have adequate convergent validity with a clinician-measure of cognition (UPDRS Item 1; $r = .39$, $p < .001$) and excellent discriminant validity from measures of motor symptoms (UPDRS-Part III Total; $r = .08$, $p = .41$) and disease severity (Hoehn and Yahr; $r = .11$, $p = .26$).
5. The Montreal Cognitive Assessment (MoCA) will be administered at the baseline (pre-intervention) assessment as a measure of general cognition and will be used as a covariate in the statistical analyses (please see Data Analysis section below). The MoCA is a suitably accurate, brief (10-minute) test of cognitive impairment in PD and has established cut-offs for both PD-MCI and PDD.⁶⁹
6. Cognitive Problems and Strategies Assessment (CPSA)³⁸. The Strategies Assessment section of the CPSA will be used as an assessment of compensatory strategies used by the individual. This questionnaire was found to be sensitive to the use of cognitive strategies after cognitive rehabilitation (CogSMART) participation³⁸. The CPSA takes 8-10 minutes to complete.
7. Parkinson’s disease Cognitive Rating Scale (PD-CRS; Pagonabarraga et al., 2008). This is a cognitive scale specifically designed for individuals with Parkinson’s disease. The assessment has a total of 9 tasks meant to assess attention, working memory, alternating and action verbal fluency, clock drawing, and verbal memory and takes approximately 15 minutes to administer.

Quality of Life, Health Status, and Neuropsychiatric Symptom Assessment:

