Data Analysis: Preliminary analyses will begin with an examination of the distribution of variables to assess their characteristics (means, standard deviations, skewness), to provide descriptive statistics of the study population, and to allow assessment of randomization. Continuous measures will be tested for normality and homogeneity of variance. Non-normally distributed variables will be transformed to meet the normal distribution assumption for linear effects models. Analyses will include tests of randomization and comparability across conditions. Randomization will be tested by performing a series of t-tests and chi-square tests to compare the groups on demographic and initial clinical variables. Pre-specified baseline variables including age, education, gender, severity and duration of illness, and motor symptoms will be considered as potential covariates (as fixed effects) in the multivariate analyses. Any other variables (e.g., baseline cognition as assessed by the MoCA, medications) on which the groups differ initially will also be explored as covariates in subsequent analyses, as described below. In the case of missing data, appropriate data analytic techniques will be used, which may include deletion, imputation, inclusion of an indicator of missing values, or pattern-mixture modeling. Outcomes will be analyzed using SPSS release 16 (SPSS, 2007), and open source statistical software R⁸¹.

As an exploratory aim, we will recruit 60 additional individuals to complete the protocol as described above and in addition, participate in two (pre/post) hour-long brain imaging (fMRI) sessions. The imaging sessions will consist of a structural brain scanning and participation in an fMRI cognitive task (please see below). Following the baseline evaluation, half of the participants will be randomly assigned to the intervention group ($n = 30$) and participate in the CogSMART program. The groups will be broken up to consist of approximately 5 individuals. The remaining participants ($n = 30$) will be assigned to the non-intervention/control ("supportive care") group. This group will also be broken down into groups of 5 when enrolled in the intervention. Participants will be retested by a group assignment-blinded examiner on the clinical and cognitive battery and imaging protocol following the intervention or waitlist.

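### Phase II does not fix its primary model: MoCA is a firm covariate in one place and conditional on baseline tests in another, and the role of baseline Matrix Reasoning is never stated

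*Combined protocol and SAP*

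**What the plan says.** All references are to the combined protocol and SAP.

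- **MoCA, measure description** (Section 9, Phase II, Cognitive Function and Cognitive Strategy Assessment, item 5): the baseline MoCA "will be used as a covariate in the statistical analyses". No condition is attached, and the reader is referred to the Data Analysis section.
- **MoCA, Data Analysis** (Section 9, Phase II): "Any other variables (e.g., baseline cognition as assessed by the MoCA, medications) on which the groups differ initially will also be explored as covariates". The initial comparison is described as "Randomization will be tested by performing a series of t-tests and chi-square tests", without a threshold.
- **Other covariates** (same paragraph): age, sex, schooling, motor symptoms, and the severity and length of illness are labelled pre-specified, but they "will be considered as potential covariates (as fixed effects) in the multivariate analyses".
- **Forward reference** (same paragraph): imbalanced variables are to be "explored as covariates in subsequent analyses, as described below". The text then turns to missing data, software, and the imaging, exercise and saliva aims. No model is given.
- **Primary outcome** (Section 6, Phase II, Hypothesis 1): Matrix Reasoning, with the hypothesis worded as a larger improvement than supportive care at 10 weeks.
- **Baseline data** (Section 9, Phase II, Procedures): "Within one to 1.5 weeks prior to beginning the group, participants will be tested by a research assistant blinded to group assignment". The cognitive battery includes Matrix Reasoning.
- **Phase I, for comparison** (Section 9, Phase I): "We will compare the treatment and control groups on baseline and three-month change scores", and group differences "will also be determined via repeated measures (RM) ANCOVAs". Phase II neither repeats this nor refers back to it.

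**The concern.** Two statements about the same covariate give different instructions, and the first points to the second as its authority. An analyst following the measure description always includes MoCA. One following Data Analysis includes it only after an observed imbalance.

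The test-based rule is weak in itself. A baseline significance test asks whether the arms differ on a variable, not whether the variable predicts the outcome, and it lets the data choose the primary model. Labelling six variables pre-specified settles little when none is committed to the model.

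The larger gap is baseline Matrix Reasoning. It is likely to be the strongest available predictor of the 10-week score and is already collected. A hypothesis about improvement, together with a passing mention of linear models, fits a change score, a baseline-adjusted comparison or a repeated-measures model. These differ in precision. They also differ in bias if the arms are not comparable at entry.

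**Working it through.** **Reading the text.** No Phase II sentence chooses among change score, baseline adjustment and repeated measures. The withheld pages fall outside Section 9, so they do not explain the gap.

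**Inputs.** From the protocol: 55 per group. The protocol gives no alpha, effect size, SD or correlation for Phase II, so there is no planned figure to reproduce. Assumed: d = 0.5 SD, two-sided 0.05, equal variances at both visits, correlation r between baseline and 10-week score of 0.3 to 0.8, no clustering, no attrition. Steps 1 to 3 also assume comparable arms; step 4 relaxes that.

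**1. Variance.** In units of the outcome variance, the per-person residual variance is 2(1 - r) for a change score and 1 - r² after baseline adjustment. The ratio of adjusted to change is (1 - r²) / [2(1 - r)] = (1 + r)/2. This needs neither d nor alpha.

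**2. Power.** Non-central t with non-centrality d / [f × √(2k/55)].
- Change score: f = √(2(1 - r)), k = 1, 108 df.
- Adjusted: f = √(1 - r²), k = 1 + 1/106 (average cost of chance imbalance), 107 df.
- Example at r = 0.5: √(2/55) = 0.1907. Change: 0.5/0.1907 = 2.62. Adjusted: 0.5/(0.866 × 0.1907 × 1.0047) = 3.01.

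| r | Variance ratio, adjusted / change | Reduction | Power, change | Power, adjusted | Gain |
|---|---|---|---|---|---|
| 0.3 | 0.65 | 35% | 59.3% | 77.4% | about 18 points |
| 0.5 | 0.75 | 25% | 73.8% | 84.8% | about 11 points |
| 0.7 | 0.85 | 15% | 91.8% | 95.2% | about 3 points |
| 0.8 | 0.90 | 10% | 98.4% | 99.1% | under 1 point |

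**3. MoCA added to baseline Matrix Reasoning.** With partial correlation q, multiply f by √(1 - q²); use 106 df and k = 1 + 2/105.

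| r | Without MoCA | q = 0 | q = 0.1 | q = 0.2 | q = 0.3 |
|---|---|---|---|---|---|
| 0.3 | 77.4% | 77.0% | 77.4% | 78.6% | 80.7% |
| 0.5 | 84.8% | 84.4% | 84.8% | 85.8% | 87.6% |
| 0.7 | 95.2% | 95.0% | 95.2% | 95.7% | 96.5% |

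The change runs from -0.4 points (77.0 - 77.4) to +3.3 points (80.7 - 77.4).

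**4. Allocation.** Section 9, Phase II, Procedures assigns the first five enrolled to one arm, the next five to the other, and so on. That is deterministic, so a lasting difference between arms cannot be excluded. Suppose one arm sits s higher at both visits and treatment does nothing. The change score gives s - s = 0. Baseline adjustment gives s - r × s = s(1 - r). For an assumed s of 0.2 SD and r = 0.3 / 0.5 / 0.7, that bias is 0.14 / 0.10 / 0.06 SD. In simulation (55 per arm, 20,000 trials) the false-positive rate is about 12% / 9% / 7% for baseline adjustment and about 5% for the change score.

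**The case against.** **The MoCA description defers to Data Analysis, so it may be shorthand rather than a rival rule.** That is a fair reading, and either direction would resolve the conflict. It does not remove the need to choose, because the deferring sentence is unconditional and the governing one is not.

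**The protocol does name covariates.** A reader might infer that nothing was pre-specified. That is too strong: six variables carry that label. What is missing is a commitment to use them or a rule for entry.

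**Baseline tests are informative here.** The usual argument is that under random allocation such tests detect only chance. It cannot be used without qualification, because alternating fives are not random and a difference may be systematic. This stands. The case against the rule rests instead on its ignoring prognostic value and leaving the model to the data.

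**The gain depends on r.** This also stands. Eighteen points needs r = 0.3; for a test the protocol describes as reliable, a higher r is plausible and the gain over a change score shrinks to a few points or less.

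**Change scores are safer under a stable arm difference.** Correct, as step 4 shows. Baseline adjustment must not be presented as a repair for the allocation.

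A reader might also infer that the test-based rule inflates type I error. The calculations do not support this: with MoCA gated on top of baseline Matrix Reasoning, simulated null rejection under random allocation was 4.6% to 4.9%. Choosing the most favourable of several models would inflate it, but nothing in the protocol says that will be done.

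**Conclusion.** The point holds as one of consistency and pre-specification, and the plan should be changed. Three findings rest on the text alone: the two statements on MoCA conflict, the six named variables have no entry rule, and the role of baseline Matrix Reasoning in the primary analysis is unstated.

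The size is illustrative. Against a change score, baseline adjustment removes 35% / 25% / 15% of the variance at r = 0.3 / 0.5 / 0.7, subject to the assumptions listed in the working. Both arms meet in groups of five and some attrition is likely, so the power figures are a guide to direction and rough size only; differences below a point carry no weight.

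It would be tempting to say that the MoCA conflict threatens the trial's power. The figures do not bear that out. Precision depends mainly on baseline Matrix Reasoning.

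**What to change.** Before unblinding, amend the Phase II Data Analysis text as follows.

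1. State one primary model for 10-week Matrix Reasoning that always includes baseline Matrix Reasoning, as a covariate or as the baseline response in a named repeated-measures model. If repeated measures is chosen, say whether baseline means are held equal between arms. With free means and two visits it reproduces the change-score result.
2. Use each secondary outcome's own baseline in its model.
3. Fix MoCA's role in advance and make the two places agree. Always including it is consistent with the measure description.
4. Replace the potential covariates with a short fixed list drawn from the variables already named.
5. Drop baseline t-tests and chi-square tests as the rule for covariate entry, and show baseline data descriptively by arm.
6. Because arms are assigned in alternating fives, add a sensitivity analysis using change scores or repeated measures with free baseline means. Say that baseline adjustment reduces a stable arm difference but does not remove it.

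The cost is wording and a few degrees of freedom; the variables are already collected. Under the same assumptions, MoCA costs at most about 0.4 power points if it adds nothing. In simulation, three uninformative covariates cost about 1 point and seven about 1.5 to 3, which is why the list should be short.
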